5.7.9. Duration of Adverse Events

Duration of Adverse Events (in DD:HH:MM) will be calculated as:

Duration of Adverse Event = (Resolution Date and Time) – (Onset Date and Time)

Where time is missing, only dates will be used. If a resolution or onset date is missing or incomplete, no duration will be derived.

5.7.10. Change from Baseline

For safety and efficacy, CFB will be calculated as (post-baseline result – baseline result), and percentage change from baseline (%CFB) will be calculated as 100 x (post-baseline result – baseline result)/baseline result.

Changes from baseline will use Baseline (Derived), including where Baseline (Derived) uses the imputed LLQ value.

Change from baseline comparisons for categorical variables will use Baseline (Derived) and will be displayed using shift-tables that display the frequency and percentage of subjects within each category at baseline and at any specified time points.

If Baseline (Derived) is missing then the CFB and %CFB will also be set to missing, unless otherwise stated. Only subjects with a value at both the Baseline (Derived) visit and the specific post-baseline visit will be presented.

5.7.11. Observed Cases (OC) and Last Observation Carried Forward (LOCF) and Outliers

Not applicable for this study. Missing data will not be imputed.

Outliers will be included in all outputs.

5.7.12. Completers

Not applicable for this study.

5.7.13. SF-36

SF-36 version 2 will be used in the study and will be scored as per the instructions for the RAND 36-Item Health Survey 1.0 - (https://www.rand.org/health-care/surveys_tools/mos/36-item-short-form/scoring.html).

There are eight health domains (Vitality, Physical Functioning, Bodily Pain, General Health Perceptions, Physical Role Functioning, Emotional Role Functioning, Social Role Functioning and Mental Health) and psychometrically-based physical component summary (PCS) and mental component summary (MCS) scores. Scoring will be undertaken using the commercial software by QualityMetric. The scores provided by QualityMetric will be used for the data summary.

5.7.14. **BPI-SF**

Two scores are calculated from the Brief Pain Inventory -(https://www.mdanderson.org/documents/Departments-and-Divisions/Symptom-Research/BPI_UserGuide.pdf). The pain severity score is calculated as the mean of the non-missing values for questions 3 (worst pain), 4 (least pain), 5 (average pain) and 6 (current pain).

The pain interference score is calculated as the mean of the non-missing values for questions 9a, b, c, d, e, f and g, which represent pain interference with general activity, mood, walking ability, normal work, relations with other people, sleep, and enjoyment of life. Subjects who answer fewer than four questions will not have a pain interference score derived.

5.7.15. Derivations for Adverse Events

A treatment-emergent adverse event (TEAE) will be any adverse event occurring after a subject has started auxiliary medications, i.e., started mobilization with G-CSF. This includes: i) any AE that emerges after start of mobilization with G-CSF (having been absent before start of mobilization with G-CSF) or ii) any AE that although present before G-CSF, worsens after start of mobilization with G-CSF (in this case, there will be a new AE entered after worsening).

Where the start date/time of an AE is partial or missing and the end date/time is on or after the date/time of start of mobilization with G-CSF, or both the start and end dates/times are missing, then a "worst-case" scenario will be assumed, thus the AE is assumed to have occurred after the start of mobilization with G-CSF (i.e., treatment-emergent) unless a partial start or end date indicates otherwise. When partial dates are present in the data, both a partial start date and/or a partial end date will be evaluated to determine whether it can be conclusively established that the AE started prior to the start of mobilization with G-CSF or ended prior to the start of mobilization with G-CSF. If it cannot be conclusively established that the AE started prior to the start of mobilization with G-CSF based on the partial start and/or end dates, then the AE will be considered as treatment-emergent.

The following table presents an algorithm for the determination of whether a given AE will be considered treatment emergent or not:

Start date of AE	End date of AE	Action
Known	Known, Partial	If start date/time < start date/time of
	or Missing	mobilization with G-CSF, then not TEAE
		Otherwise, if start date/time \geq mobilization with
		G-CSF start date/time, then TEAE
Partial, but known	Known, Partial	Not TEAE
components show that it	or Missing	
cannot be on or after		
mobilization with G-CSF		
start date/time		
Partial, could be on or	Known	If end date/time < mobilization with G-CSF
after mobilization with		start date/time, then not TEAE
G-CSF start date/time		
OR Missing		If end date/time \geq mobilization with G-CSF
		start date/time, then TEAE
	Partial	Temporarily impute end date/time as latest
		possible date/time (i.e., 23:59 on last day of
		month if day and time unknown or 31st

 Table 3: Algorithm for Treatment Emergence of Adverse Events

Start date of AE	End date of AE	Action
		December 23:59 if day and month and time are
		unknown), then:
		If imputed end date/time < mobilization with G-
		CSF start date/time, then not TEAE
		If imputed end date/time \geq mobilization with G-
		CSF start date/time, then TEAE
	Missing	Assumed TEAE

These imputations will only be used to determine treatment emergence for inclusion in table summaries; the reported missing or partial dates will be presented in listings.

AEs will be tabulated by one of the seven study periods based on the onset date/time of AEs:

- Pre-Mobilization: started before first dosing of G-CSF
- Auxiliary Medications:
 - Mobilization:
 - G-CSF: started (or worsened) on or after first dosing of G-CSF for Mobilization until start of apheresis
 - For any subject who received Mobilization twice, the study period between the start of the second Mobilization until the start of the second apheresis will be captured as Mobilization #2

o Apheresis:

- started (or worsened) on or after start of apheresis until the end of the last apheresis
 - For any subject who received Apheresis twice, the study period between the start of the second apheresis until the end of the second apheresis will be captured as Apheresis #2
- Post-Apheresis: started (or worsened) after the end of the last apheresis and before first dosing of anti-convulsant medication given for prophylaxis ahead of busulfan
 - For any subject who received Mobilization twice, the study period between the end of the first apheresis and the start of Mobilization #2 will be captured as Post-Apheresis
 - The study period between the end of the second apheresis and the first dosing of anti-convulsant medication given for prophylaxis ahead of busulfan will be captured as Post-Apheresis #2

- For any subject who received Mobilization but did not proceed to receive conditioning or AVR-RD-02, the study period after the end of Apheresis will be captured as Post-Apheresis
- Conditioning: started (or worsened) on or after first dosing of anti-convulsant medication given for prophylaxis ahead of busulfan and before infusion of AVR-RD-02
- AVR-RD-02 Infusion: started (or worsened) on or after the start of infusion of AVR-RD-02
- Post-AVR-RD-02 Infusion Follow-Up: started (or worsened) after the end of AVR-RD-02 infusion

The date and time of AEs are captured, as well as date and time for G-CSF, plerixafor, apheresis, busulfan and AVR-RD-02 infusion. Therefore, when assigning AEs to a study period, the time (HH:MM) of the onset (or worsening) of the AE will be compared to the time of the auxiliary medication or AVR-RD-02, e.g., on Day 1, an AE with onset time prior to the start time of AVR-RD-02 infusion will be assigned to the Conditioning study period. Where time is missing or incomplete, the AE will be assigned to the study period using the date alone, e.g., on Day 1, an AE on Day 1 with onset time missing will be assigned to the AVR-RD-02 infusion study period.

If an adverse event continues into subsequent periods it will only be counted in the period in which it first occurred, in order to avoid double counting.

6. TREATMENT COMPARISONS

6.1. Data Display Treatment and Other Sub-Group Descriptors

The Analysis Population used will be presented on all figures and tabulations.

Adverse Events will be summarized by System Organ Class (SOC) and Preferred Term (PT). Additionally, AEs will be summarized by study period (Pre-Mobilization, Auxiliary Medications, AVR-RD-02 Infusion, and Post-AVR-RD-02 Infusion Follow-Up). The Auxiliary Medications study period will be further broken down into Mobilization, Apheresis, Post-Apheresis, and Conditioning. The following labels for study period will be used on applicable AE tabulations:

- All Adverse Events
- Pre-Mobilization
- Auxiliary Medications
 - Mobilization
 - i. Mobilization #2 for any subject who received Mobilization twice
 - > Apheresis
 - i. Apheresis #2 for any subject who received Apheresis twice
 - > Post-Apheresis
 - i. Post-Apheresis #2 for any subject who received Mobilization/Apheresis twice
- Conditioning
- AVR-RD-02 Infusion
- Post-AVR-RD-02 Infusion Follow-Up

7. GENERAL CONSIDERATIONS FOR DATA ANALYSES

The listings and summary tables for the disposition, safety and efficacy data will be the responsibility of the study Biostatistician.

The currently supported version of SAS[®] software will be used to perform all data analyses. The actual SAS[®] version used will be presented in the Clinical Study Report.

All data in the database will be presented in the data listings. Unless otherwise stated, all listings will be sorted by subject number and assessment date/time. In the listings, subject number will be of the format 123456.

7.1. Multicenter Studies

Data from all participating sites will be pooled.

7.2. Other Strata and Covariates

Not applicable for this study.

7.3. Examination of Subgroups

Not applicable for this study.

7.4. Multiple Comparisons and Multiplicity

Not applicable for this study as there are no formal hypothesis tests being conducted.

7.5. Data handling conventions

7.5.1. Premature Withdrawal and Dropouts

For subjects who are withdrawn or dropout from the study prior to study completion, all data collected will be listed and included in data summaries. Early termination data will be mapped using visit windows.

7.5.2. Additional/Unscheduled Assessments

Generally, missing dates/times will not be imputed. Adverse events with missing or partial dates will be handled such that in the absence of contradictory information an AE is classified based on the study period closest to the AE onset. Adverse events will be assigned to each study period according to Section 5.7.15.

Unscheduled assessments will be considered when applying visit windows (and for derived study periods) and will also contribute to the end of study value, or best/worst case value where required (e.g., shift table).

When deriving a subject level statistic (e.g., maximum value post-baseline), all values should be included (including scheduled, unscheduled, retest and early discontinuation data) regardless of whether they appear in a corresponding visit-based summary.

Listings will include scheduled, unscheduled, retest and early discontinuation data.

7.5.3. Assessment Windows

Visit windows as defined below will be applied and applied in tables and/or figures:

 Table 4: Visit Window Assignment

Assigned Study Day (Inclusive)		Visit Assigned	Target Study	Target
		v Isit Assigned	Day	Study Week
From	То			
1	1	Day 1 (Transplant)	1	1
2	2	Day 2 (W1)	2	1
3	3	Day 3 (W1)	3	1
4	4	Day 4 (W1)	4	1
5	5	Day 5 (W1)	5	1
6	6	Day 6 (W1)	6	1
7	7	Day 7 (W1)	7	1
8	12	Day 10 (W2)	10	2
13	22	Day 14 (W2)	14	2
23	45	Day 30 (W5)	30	5
46	75	Day 60 (W9)	60	9
76	105	Day 90 (W13)	90	13
106	135	Day 120 (W18)	120	18
136	165	Day 150 (W22)	150	22
166	225	Day 180 (W26)	180	26
226	318	Day 270 (W39)	270	39
319	413	Day 365 (W52)	365	52

Inclusion within the time window should be based upon the actual date of the visit rather than the intended date so that all unscheduled visit data (including unscheduled early termination visits) have the potential to be included.

In the case where two or more measurements fall within the same visit window, the available measurement closest to the planned visit date will be used. If two measurements are equidistant from the planned visit date then the earlier value will be used. If multiple measurements occurred on the same date, and the time (HH:MM) of each assessment is available, then these will be reviewed on a case-by-case basis. If time is unavailable, the mean of the measurements will be taken. In the case of a retest where there is clear evidence to suggest that the retest was done due to erroneous data, then the retest value will be used. Otherwise, the mean of the measurements will be used.

Scheduled, unscheduled, retest and early discontinuation data will be included when mapping to visit windows.

7.5.4. Visit/Study Period Mapping and Labels

Within **Tables**, **Figures** and **Listings**, the mapping and derived visit labels in Table 4 will be used from date of AVR-RD-02 infusion onwards.

In order to aid interpretation of the temporal nature of adverse events and medications, derived study periods are applied. If it is deemed necessary for other data, eg clinical laboratory values, vital signs, etc., then derived study periods will also be applied as described below.

Prior to the date of AVR-RD-02 infusion, the below mapping and derived study period labels will be used in **Listings**:

- Pre-Mobilization: date is before first dosing of G-CSF for Mobilization
- Auxiliary Medications:
 - Mobilization:
 - G-CSF: started (or worsened) on or after first dosing of G-CSF for Mobilization until start of apheresis
 - For any subject who received Mobilization twice, the study period between the start of the second Mobilization until the start of the second apheresis will be captured as Mobilization #2
 - Apheresis:
 - started (or worsened) on or after start of apheresis until the end of the last apheresis
 - For any subject who received Apheresis twice, the study period between the start of the second apheresis until the end of the second apheresis will be captured as Apheresis #2
 - Post-Apheresis: started (or worsened) after the end of the last apheresis and before first dosing of anti-convulsant medication given for prophylaxis ahead of busulfan
 - For any subject who received Mobilization twice, the study period between the end of the first apheresis and the start of Mobilization #2 will be captured as Post-Apheresis
 - The study period between the end of the second apheresis and the first dosing of anti-convulsant medication given for prophylaxis ahead of busulfan will be captured as Post-Apheresis #2
 - For any subject who received Mobilization but did not proceed to receive conditioning or AVR-RD-02, the study period after the end of Apheresis will be captured as Post-Apheresis
 - Conditioning: date is on or after first dosing of anti-convulsant medication given for prophylaxis ahead of busulfan and before date of infusion of AVR-RD-02

Listings will present both protocol visit/study day and also derived study period/study day. Baseline (Derived) will also be included. Unscheduled, retest and early discontinuation data prior to the day of AVR-RD-02 infusion will be included when mapping to the above study period labels for **Listings**.

In **Tables** and **Figures**, the following mapping and study period labels will again be used prior to the day of AVR-RD-02 infusion:

- Pre-Mobilization: date is before first dosing of G-CSF for Mobilization
- Auxiliary Medications:
 - Mobilization:
 - G-CSF: started (or worsened) on or after first dosing of G-CSF for Mobilization until start of apheresis
 - For any subject who received Mobilization twice, the study period between the start of the second Mobilization until the start of the second apheresis will be captured as Mobilization #2
 - Apheresis:
 - started (or worsened) on or after start of apheresis until the end of the last apheresis
 - For any subject who received Apheresis twice, the study period between the start of the second apheresis until the end of the second apheresis will be captured as Apheresis #2
 - Post-Apheresis: started (or worsened) after the end of the last apheresis and before first dosing of anti-convulsant medication given for prophylaxis ahead of busulfan
 - For any subject who received Mobilization twice, the study period between the end of the first apheresis and the start of Mobilization #2 will be captured as Post-Apheresis
 - The study period between the end of the second apheresis and the first dosing of anti-convulsant medication given for prophylaxis ahead of busulfan will be captured as Post-Apheresis #2
 - For any subject who received Mobilization but did not proceed to receive conditioning or AVR-RD-02, the study period after the end of Apheresis will be captured as Post-Apheresis
 - Conditioning: date is on or after first dosing of anti-convulsant medication given for prophylaxis ahead of busulfan and before date of infusion of AVR-RD-02

For **Tables** and **Figures**, scheduled, unscheduled, retest and early discontinuation data will be included when mapping to study periods. In the case where daily measurements were not scheduled per protocol, but two or more measurements still fall within the same study period, then these will be reviewed on a case-by-case basis. In the case of a retest where there is clear evidence to suggest that the retest was done due to erroneous data, then the retest value will be used.

In the case where daily measurements were scheduled per protocol, e.g., daily measurements during Mobilization, Apheresis or Conditioning, then each individual scheduled assessment will be included separately in **Tables** and **Figures** under the appropriate study period label, e.g. Mobilization (Day 1).

Baseline (Derived) will also be included in all Tables and Figures.

Figures presenting CFB for efficacy will only include Baseline (Derived) and post-AVR-RD-02 visits derived as per Table 4.

Figures presenting CFB for safety will include Baseline (Derived) and post-baseline visits.

Shift Tables presenting shifts from baseline for safety will include Baseline (Derived) and post-baseline visits.

For subjects who are withdrawn or dropout from the study prior to study completion, all data collected will be listed and included in tables and/or figures. Early termination data will be mapped using visit windows to the derived visits in Table 4 or to the derived study periods described above.

7.6. Derived and Transformed Data

The required endpoints and variables will be derived by the statistical programmers at AVROBIO, Inc. using the derivations specified in Section 5.7 of this SAP.

8. STUDY POPULATION

All disposition, baseline and demographic data will be listed using the All Subjects population.

8.1. Disposition of Subjects

A disposition listing will present date of informed consent, date of enrollment, date of study completion or early termination, the primary reason for early discontinuation, if applicable, duration of follow-up (using time since AVR-RD-02 infusion), if applicable, and whether included in each population and reasons for exclusion, for each subject.

A listing of whether or not all inclusion and exclusion criteria were met and if not, which criteria were not met, by subject, will also be presented.

8.2. **Protocol Deviations**

A protocol deviation is any change, divergence, or departure from the study design or procedures defined in the protocol that occur during the conduct of a clinical study (ICH E3 Questions and Answers). Protocol deviations should be defined as either "Important protocol deviations" (IPDs) per the ICH E3 guidance "Structure and content of clinical study reports" or "Other Study Deviations". Important protocol deviations (IPDs) are defined as a subset of protocol deviations that may significantly affect the completeness, accuracy, and/or reliability of the study data or that may significantly affect a subject's rights, safety, or well-being, and include:

- Any clinical condition that in the Investigator's opinion could become dangerous for the subject and prevent the good conduct of the clinical trial;
- Protocol violation that could compromise the quality of study data such as: use of erythropoietin, use of biological agents potentially modifying erythropoiesis, enrolment into interventional clinical trials, bone marrow transplantation;
- Occurrence of new diseases that could influence the treatment efficacy, for which AVRO-RD-02 is contraindicated or that are treated with a medication that is not permitted as a concomitant medication.

The process of identifying protocol deviations as well as identification of IPDs, review and classification are specified in the Protocol Deviation Management Plan.

The need for any supplementary analyses resulting from protocol deviations will be determined following review of the protocol deviations ahead of database lock and will be documented prior to the primary analysis being conducted.

The Sponsor or designee will be responsible for producing the final protocol deviation file in collaboration with **and the data monitoring group as applicable; this file will include a description of the protocol violation and clearly identify whether or not this violation warrants exclusion from the aforementioned populations.**

All protocol deviations will be listed. The type of protocol deviation, the description, importance and classification, actions taken, and the date it occurred will be included. The potential impact of notable protocol deviations deemed important by the study team will be discussed in the CSR.

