2.2.2. Safety Endpoints

2.2.2.1. Primary Safety Endpoints

Primary safety endpoints:

- Incidence and severity of AEs, incidence of serious adverse events (SAEs), and incidence and severity of AEs of interest, including drug-product related AEs, infections, and malignancy
- Change from Baseline in clinical laboratory values relevant to safety
- Change from Baseline in vital signs
- Change from Baseline in ECG findings and Weeks 26 and 52

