5.5.2. Safety Population

The Safety population will consist of all enrolled subjects who receive any auxiliary medication (G-CSF, plerixafor, busulfan, or anti-convulsant) or AVR-RD-02. This population will be used for the summaries of all safety data.

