5.5.3. Infused Population

The Infused population will consist of all enrolled subjects who receive all auxiliary medications and AVR-RD-02. This population will be used for the summaries of all efficacy and safety data.

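### SAP 8.2 allows a protocol deviation to exclude a subject from the Safety and Infused populations, in conflict with the definitions in SAP 5.5

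*SAP*

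**What the plan says.** SAP 5.5 defines three populations. All Subjects is everyone who consented. For the second, "The Safety population will consist of all enrolled subjects who receive any auxiliary medication" or AVR-RD-02. For the third, "The Infused population will consist of all enrolled subjects who receive all auxiliary medications and AVR-RD-02". None of the definitions mentions protocol deviations. SAP 10.4 states that these three sets replace those in the protocol, so the Per Protocol set of protocol 11.3 is gone.

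SAP 8.2 defines a deviation as a departure from the design or procedures of the study, and important deviations as a subset of these. It then lists three kinds of important deviation:

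- "Any clinical condition that in the Investigator's opinion could become dangerous for the subject and prevent the good conduct of the clinical trial";
- violations that could compromise data quality, with examples that include "enrolment into interventional clinical trials, bone marrow transplantation";
- "Occurrence of new diseases that could influence the treatment efficacy", or that contraindicate the product or are treated with a medication that is not permitted.

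The sponsor or its designee produces the final deviation file, which must "clearly identify whether or not this violation warrants exclusion from the aforementioned populations". The SAP gives no criteria for that judgement. Identification, review and classification of deviations are left to a Protocol Deviation Management Plan.

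**The concern.** Membership of the Safety and Infused populations should follow from facts fixed by treatment: what the subject received. SAP 5.5 says so. SAP 8.2 adds a second, discretionary route out of the same populations, with no criteria in the SAP, and two of its three kinds of important deviation are worded as things that happen to a subject rather than departures from procedure.

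The primary safety endpoints include "incidence and severity of AEs of interest, including drug-product related AEs, infections, and malignancy". A serious illness after infusion could thus be a primary outcome and, on a loose reading of 8.2, also a ground for considering exclusion. An exclusion related to outcome would tend to favour the product, because the subject most likely to be considered is one who did badly. Even with no such intent, a programmer working from 5.5 and one working from the deviation file could arrive at different denominators.

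**Working it through.** The plan gives no power, alpha or sample-size calculation to reproduce: the 8 to 16 subjects were chosen without statistical considerations (SAP 3.2.1) and no tests are planned (SAP 2.3). The check is mainly a comparison of sections.

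**1. Which populations can the clause reach?** The SAP defines only All Subjects, Safety and Infused (5.5.1 to 5.5.3). In the protocol, only the Per Protocol set used deviations (protocol 11.3), and SAP 10.4 replaced it. No adherence-based set remains for the clause to act on.

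**2. What rests on those populations?** Efficacy analyses use Infused (SAP 9). Safety analyses use Safety and Infused (SAP 10). Adverse event percentages use the population total as denominator unless stated otherwise (SAP 10.1.1.8). The main efficacy figures carry mean lines (SAP 9.1 to 9.3).

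**3. Do 5.5 and 8.2 agree?** No. Under 5.5 a subject who received all auxiliary medications and AVR-RD-02 is in Infused without further condition. Under 8.2 the same subject may be marked for exclusion. The clause also sits badly with the rest of the SAP, which keeps withdrawn subjects' data in the summaries (7.5.1) and outliers in all outputs (5.7.11).

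**4. Does timing protect the decision?** Population membership is settled before database lock (SAP 5.5). But the study is open-label, and engraftment, response and safety are assessed subject by subject as data arrive (SAP 4.1). A decision before lock is still made with outcomes known.

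**5. What stays visible?** All listings use All Subjects (SAP 5.4), and SAP 7 commits to listing all data in the database. The disposition listing gives population membership and reasons for exclusion (SAP 8.1). Adverse events, serious adverse events and deaths are listed (SAP 10.1.1.8), as are all deviations (SAP 8.2). An exclusion would alter tables, figures and means. It would not hide the subject.

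**6. Scale.** The event counts below are assumed. Suppose one subject has the event and is excluded. Incidence is x/n before and (x − 1)/(n − 1) after. Exact (Clopper-Pearson) 95% limits are added for scale only; the SAP does not plan them. For x = 0 the upper limit is 1 − 0.025^(1/n).

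| Subjects | Kept in | Excluded |
|---|---|---|
| 8 | 1/8 = 12.5% (0.3 to 52.7) | 0/7 = 0% (upper limit 41.0%) |
| 16 | 1/16 = 6.25% (0.2 to 30.2) | 0/15 = 0% (upper limit 21.8%) |

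With two affected subjects and one excluded, 2/8 = 25.0% becomes 1/7 = 14.3%, and 2/16 = 12.5% becomes 1/15 = 6.7%.

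For a mean line, assume one subject at +25% change in spleen volume and all others at −10%:

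- n = 8: (25 + 7 × (−10))/8 = −45/8 = −5.6%;
- n = 16: (25 + 15 × (−10))/16 = −125/16 = −7.8%;
- without that subject, either mean is −10%.

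The study was stopped early with only switch-stable subjects enrolled (SAP 1 and 5.1), and the documents do not give the number infused. If it was below 8, each exclusion weighs more.

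**The case against.** The strongest reply is that 8.2 removes nobody. It asks the file to say whether exclusion is warranted, and the answer may always be no. The clause reads like a remnant of the Per Protocol set. This stands: the fault is an unresolved conflict, not an instruction to exclude.

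A reader might infer that treatment failures and late toxicities are themselves important deviations. The text does not support that. The definition in 8.2 requires a departure from design or procedure. The first item needs a condition that both could become dangerous and prevents proper conduct of the trial. The third covers only new diseases with one of three stated consequences. A malignancy arising under compliant conduct does not plainly meet the definition.

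Bone marrow transplantation is named under violations and can be a genuine one, since protocol exclusion criterion 21 concerns transplanted or transplant-scheduled subjects. Protocol 7.4.5 allows treatment outside the protocol's scope after engraftment failure, SAP 10.1.2 lists rescue treatment separately, and nothing says that treatment given under 7.4.5 is a deviation.

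Some deviations do bear on membership, such as a missed auxiliary medication for the Infused population. But 5.5 already settles those cases without the clause.

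The Protocol Deviation Management Plan is not available here and may limit the discretion. A limit in a separate plan would still leave the SAP contradicting itself. Finally, the study is descriptive and not pivotal, and the sizes above are hypothetical. Both points are correct. They reduce the consequence but do not justify keeping the clause.

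**Conclusion.** The conflict between SAP 8.2 and SAP 5.5 is real and should be removed before database lock. As written, 8.2 permits a discretionary exclusion, made with outcomes known, from the populations behind the adverse event tables and the efficacy figures and mean lines. It does not require one, and nothing in the documents shows that one was made or intended.

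A reader might go further and conclude that the plan takes failures and toxicities out of the primary results. The documents do not support this: the listed items are qualified, exclusion is optional, and an excluded subject's data and the reason for exclusion would still be listed.

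One exclusion takes out 1/16 = 6.25% to 1/8 = 12.5% of a population of the planned size, and could turn a single observed event into none. This rests on two assumptions: that such an event occurs, and that the clause is used for that subject.

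**What to change.** In SAP 8.2, delete the clause on exclusion from populations. State instead that membership of the All Subjects, Safety and Infused populations is determined only by Section 5.5 and that no subject is removed for a protocol deviation.

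If the sponsor wants to show the effect of a deviation, present it as a supplementary display beside the full population. SAP 8.2 already provides for supplementary analyses prompted by deviations, decided and documented in advance.

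The list of important deviations need not be cut. A transplant or a non-permitted medication that departs from the protocol can stay on it. Add that clinical events are reported as adverse events or post-infusion interventions whether or not they are also listed as deviations.

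The cost is a few sentences before lock, with no new data and no new analysis. The one consequence is that data from deviating subjects stay in the summaries, as 5.5 already implies. If lock has passed, the CSR should state whether any subject was removed under 8.2 and, if so, give the affected tables and figures with that subject included.
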